Official Title of the study: Antimicrobial Efficacy of Xylitol, Probiotic and Chlorhexidine Mouth Rinses Among Children and Elderly Population at High Risk for Dental Caries - A Double Blind Randomized Controlled Trial.

NCT ID: NCT04399161

Date: 22-05-2020

Study Protocol

Need for the study:

World Health Organization defines dental caries as a localized, post eruptive pathological process of extreme origin involving softening of the hard tooth tissue and proceeding to the formation of cavity. The process involves bacterial interactions in plaque accumulated on the surface of the teeth. *Streptococcus mutans* in plaque is the most commonly isolated organism amidst all other cariogens. It ferments sucrose and the resulting acid causes demineralization of tooth enamel.

While mechanical methods of plaque control can maintain adequate oral hygiene, such methods are not being utilized appropriately by the population. This necessitates use of adjuncts to mechanical plaque control methods in the form of antiplaque mouth rinses. Chlorhexidine mouth rinse has been considered the most effective agent in inhibiting *Streptococcus mutans*. Although considered the gold standard, its adverse effects due to prolonged use such as staining of teeth, xerostomia, altered taste sensation, mouth/ throat irritation, antimicrobial resistance, etc. indicates the need for alternatives which have been extensively studied of late in literature.

Xylitol used as an artificial sweetener in foods, is a non-cariogenic sugar substitute. This polyalcohol cannot be metabolized by oral bacteria thereby preventing caries. The magnitude of adverse effects caused by xylitol as compared to that of Chlorhexidine is indistinct. Although studies have assessed effects of xylitol chewing gum on caries, very few have studied its efficacy as a mouth rinse.

Probiotics are live microorganisms that, when administered in adequate amounts, confer a health benefit on the host. Probiotic products seem to have an effect on the oral health of individuals by prompting beneficial bacteria to defend teeth and gums against harmful ones.

The advantages of probiotics as compared to that of chlorhexidine mouth rinse are that there are no issues of antibiotic resistance as it contains only commensal flora and there has been no proof of intoxication or allergies on consumption.

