Caries risk assessment: Individuals with high caries risk will be identified using a customized caries risk assessment tool. The caries risk assessment tool will comprise of information on socio economic status, oral hygiene practices, fluoride exposure, caries experience amongst family members, symptoms of dry mouth, quantity and frequency of intake of sweetened food and caries experience in the past and present. Each item will be scored as 0 or 1 and the total score will be obtained by summing up the scores of all the items. Any participant with total score greater than 5 will be considered to be at high risk for caries.

Method:

1. Preparation of mouth rinses
2. Baseline data collection and Microbial Analysis
3. Randomization and Group Allocation
4. Intervention
5. Post intervention data collection and Microbial Analysis

1. Preparation of mouth rinses:

Xylitol mouth rinse at 10 percentage concentration will be used. Probiotic mouth rinse will be prepared by using a commercially available probiotic product (Sporolac Plus powder- 1gm sachet containing not less than 1.5 billion cells of *Lactobacillus acidophilus*, *Lactobacillus rhamnosus*, *Bifidobacterium longum*, *Bacillus coagulans* and *Saccharomyces boulardii*). Each

sachet will be dissolved in 15 ml of water in a measuring cup and will be used as a mouth rinse. A commercially available Chlorhexidine mouth rinse (Hexidine- 0.2 percentage Chlorhexidine gluconate) containing 0.2 percentage chlorhexidine gluconate per 10 ml will be used.

2. Baseline data collection and microbial analysis:

Plaque samples will be collected from the buccal surface of a non-carious permanent maxillary first molar. Plaque collection will be done using an autoclaved scaler under daylight. The collected plaque will be stored in a pre-weighed sterile eppendorf tube. Tubes will be weighed again after plaque collection. The weight of the collected plaque (in grams) will be determined by subtracting the weight of the empty eppendorf tube from the weight of the tube with the collected plaque. The samples will be stored at - 4 degree Celsius and transported to a culture lab within an hour to avoid using transport media.

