1 ml saline will be added to the eppendorf tube and vortexed for even distribution of plaque. This mixture will be used as stock solution for serial dilutions. From the stock solution, 100 μ l will be transferred to a sterile test tube containing 900 μ l of saline and vortexed to arrive at 1:10 dilution. Similar dilutions will be prepared to obtain 1/10, 1/100 and 1/1000 dilutions. 50 μ l from each of the dilutions will be plated onto the selective medium MSB (Mitis Salivarius Bacitracin Agar) by spread plate method. After plating, the MSB (Mitis Salivarius Bacitracin Agar) agar plates will be placed in the anaerobic jar and incubated at 37 degree Celsius for 72 hours.

Colonies of *Streptococcus mutans* will be identified based on the following morphologic characteristics, a) 0.5 mm raised convex undulated colonies b) light blue colour with rough margins c) granular frosted glass appearance. The colonies will be confirmed by a catalase test (negative catalase reaction) and gram staining (gram positive cocci). Bacterial colonies will be counted manually. The standard formula for determining Colony Forming Units (CFU) will be $CFU/g = [Number\ of\ colonies \times Dilution\ factor] / [Volume\ plated\ (in\ ml) \times Amount\ of\ plaque\ (in\ g)]$

3. Randomization and Group allocation: After data collection at baseline, the study participants will be allocated to three groups, Group A, B and C, by simple random sampling (lottery method). Group A will be given Chlorhexidine mouth rinse; Group B will be given Xylitol mouth rinse and Group C Probiotic mouth rinse. The participants and the investigator will be blinded from the allocation sequence.

4. Intervention: The participants will be asked to rinse their mouth once daily (at night) for 2 minutes, using 15 ml of mouth rinse. The intervention will be carried out for a period of 14 days. Mouth rinsing will be supervised during the study period by an assistant. A record will be maintained to document regular usage of the mouth rinse and also to record any adverse effects occurring during the intervention period.

5. Post intervention data collection: After 14 days of using the mouth rinses, the same procedures will be repeated and compared with baseline.

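### Method 2 names no step to stop residual chlorhexidine acting on plaque after sampling, and the gap between last rinse and day-14 sample is not fixed: a cheap improvement against a possible one-directional bias of unknown size

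*Combined protocol and SAP*

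**What the plan says.** The Objectives and the CFU/g formula in Method 2 make a viable colony count of *S. mutans* in plaque the only efficacy measure.

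Plaque goes into a pre-weighed sterile tube with nothing added and the tube is weighed again. It is then kept cold, at a stated −4 °C, and "transported to a culture lab within an hour to avoid using transport media". After that, "1 ml saline will be added to the eppendorf tube and vortexed for even distribution of plaque". Dilution is also in saline: "100 μ l will be transferred to a sterile test tube containing 900 μ l of saline and vortexed to arrive at 1:10 dilution", with further tenfold steps to 1/1000. From each of the 1/10, 1/100 and 1/1000 tubes, 50 µl "will be plated onto the selective medium MSB (Mitis Salivarius Bacitracin Agar) by spread plate method". No neutraliser, wash or carry-over check is named at any of these steps.

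Method 5 gives the second visit in one line: "After 14 days of using the mouth rinses, the same procedures will be repeated and compared with baseline". On timing, Method 4 asks participants to "rinse their mouth once daily (at night) for 2 minutes, using 15 ml of mouth rinse", and Method 2 says that "Plaque collection will be done using an autoclaved scaler under daylight". The interval from last rinse to day-14 sample is not given.

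Method 1 gives the chlorhexidine rinse as 0.2%. It is the only one of the three rinses that is a chemical antiseptic, and the Need for the study section ranks it as the strongest inhibitor of the organism being counted.

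**The concern.** A colony count cannot tell a cell killed in the mouth from one killed in the tube. The first is the drug effect that the trial wants to measure; the second is an artefact of handling. If chlorhexidine held in day-14 plaque goes on killing after collection, the artefact falls on one arm only.

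The design does not protect against this. Baseline samples are taken before allocation (Method 3) and carry no study rinse, so using the same procedure at both visits does not cancel the effect. Randomisation and blinding do not help either, because the error travels with the assigned product. Its direction is known: the chlorhexidine before-after fall would be too large, and so would its advantage over xylitol and probiotic. Chlorhexidine is the benchmark in the stated Aim, so an equally good alternative could look inferior. Cells lost in the tube cannot be restored by any later analysis.

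**Working it through.** **1. Inputs.** From the documents: 0.2% chlorhexidine (Method 1); 1 ml saline, tenfold steps and 50 µl plated (Method 2); 12 per product per population, so 12 × 3 = 36 children and 36 elderly, which checks (Sample Size); ANOVA with Tukey at 0.05 (Statistical Analysis Plan). Assumed, because the documents give no figure: 0.2% is weight by volume (2,000 µg/ml); plaque mass *w* is 1–10 mg, at about 0.001 ml per mg; 20 ml of agar per plate; and *f*, the share of rinse strength still in plaque at sampling.

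**2. Where residue could act.** Concentration in stock = 2,000 *f* × (*w*/1000) / (1 + *w*/1000), then divided by ten per step. In µg/ml, for *w* from 1 to 10 mg:

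| *f* | Undiluted plaque | Stock | 1/10 tube | 1/1000 tube |
|---|---|---|---|---|
| 100% (extreme) | 2,000 | 2–20 | 0.2–2 | 0.002–0.02 |
| 10% | 200 | 0.2–2 | 0.02–0.2 | 0.0002–0.002 |
| 1% | 20 | 0.02–0.2 | 0.002–0.02 | 0.00002–0.0002 |

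On the plate, the extreme case is 1.98 µg/ml × 0.05 ml / 20 ml = 0.005 µg/ml. Exposure is greatest in undiluted plaque during the hour before saline is added, 100- to 1,000-fold lower in the stock, and very small on the agar. The tube is the credible route.

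**3. Direction.** Let *k* be the share of viable *S. mutans* lost after sampling in the chlorhexidine arm at day 14. The measured log10 count is the true one plus log10(1 − *k*). Baseline and the other two arms have no such term, so it passes whole into the paired change and into both chlorhexidine contrasts. For *k* = 30%, 50% and 70% the shift is −0.155, −0.301 and −0.523 log10.

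**4. What a given loss would do, if it occurred.** Simulation of 40,000 trials: three arms of 12, normal log10 values, no true difference, and an assumed SD of 1.0 or 0.5 log10. The result is the chance that Tukey wrongly favours chlorhexidine over at least one comparator:

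| Assumed *k* | SD 1.0 | SD 0.5 |
|---|---|---|
| 0 | 1.8% | 1.9% |
| 30% | 4.4% | 9.5% |
| 50% | 8.9% | 28.1% |
| 70% | 21.7% | 70.5% |

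This table is conditional. Neither *k* nor the SD is in the documents, nothing links *f* in step 2 to *k* here, and the Statistical Analysis Plan does not state a log scale. It shows sensitivity to a loss, not the size of the loss.

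**The case against.** The strongest reply is that there may be nothing left to neutralise. Rinsing is at night and sampling in daylight, so hours of clearance probably intervene. Residue in undiluted plaque is also no stronger in the tube than it was in the mouth a moment earlier. Cells alive at sampling have already survived that exposure at body temperature, and only extra killing in up to one cold hour, plus bench time in a far weaker stock, is artefact. This stands as a limit on size. It does not close the gap: the interval is inferred from two separate remarks, no minimum is set, and the plan has no check that would reveal a loss.

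A reader might infer three stronger things that the documents do not support:

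- *Chlorhexidine goes on suppressing colonies on the plate.* The strongest tube plated is 1/10, and step 2 shows how little free agent reaches the agar.
- *The trial has a high false-claim rate in favour of chlorhexidine.* The larger percentages in step 4 follow from an assumed loss and an assumed SD.
- *The three dilutions already plated would expose the problem.* Cells killed in the tube are missing from every dilution alike, so counts would still fall tenfold. Crowding on the 1/10 plate would also break the ratio for an unrelated reason.

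A fair practical objection is that a neutraliser can damage the assay if added at the wrong point. Fluid in the tube before the first weighing would mean finding milligrams of plaque (assumed) by difference against about 1 g of liquid. A suspended sample might also freeze at the stated storage temperature. Both bear on how the fix is written.

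**Conclusion.** The point holds as a low-cost improvement. No step in Method 2 stops residual chlorhexidine after sampling, and Methods 4 and 5 leave the interval from last rinse to day-14 sampling open. Any killing after sampling would favour chlorhexidine in both the paired and the between-arm tests, and would survive every protection in the design.

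Its size cannot be derived from the documents. It depends on residue at sampling, on how much extra killing that residue causes in the cold tube and the stock, and on between-person variability, none of which is given. It may be near zero. The bias is possible, not shown, and this point alone gives no ground for calling a chlorhexidine advantage an artefact.

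**What to change.** 1. In Method 2, replace the plain suspension saline with 1 ml saline containing a validated chlorhexidine neutraliser. Add it after the second (dry) weighing and as soon after collection as possible, identically in all three arms and at both visits. The volume, dilution factors, CFU/g formula, laboratory blinding and sample size are unchanged. State where the second weighing takes place: if it is only at the laboratory, the neutraliser protects the stock but not the hour before it.
2. In Method 5, fix the interval from last rinse to day-14 sampling, the same in all arms, and record it for each participant.

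The cost is one reagent, a short protocol edit and one recorded time. The laboratory must confirm once that the neutraliser does not affect *S. mutans* growth on MSB agar, and that the suspended sample does not freeze at the stated storage temperature. Adding fluid early also departs from the plan's dry, fast transport, so the text on avoiding transport media should be adjusted to match.

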Antimicrobial efficacies of probiotics and xylitol mouth rinses have not been compared till date. Also their effects on the young and elderly population have not been compared. Hence the purpose of the present study is to compare the antimicrobial efficacies of probiotic and xylitol mouth rinses with the gold standard in children and elderly population.

Aim of the study:

To compare the antimicrobial efficacy of probiotic and xylitol mouth rinses with chlorhexidine (gold standard) among children and elderly population at high risk for dental caries.

Objectives of the study:

1. To assess *Streptococcus mutans* levels at baseline and 14 days after intervention in children and elderly population.
2. To compare efficacies of the 3 mouth rinses in reducing *Streptococcus mutans* levels in children and elderly.

Materials and methods:

Source of data: Residential school children aged 5-12 years at high risk for caries. Elderly population above 60 years residing in old age homes at high risk for caries.

Eligibility Criteria:

Inclusion Criteria:

1. Children aged 5-12 years at high risk for caries.
2. Elderly citizens (above 60 years) at high risk for caries.
3. Those willing to participate in the study and consented.
4. Not under antimicrobial therapy or used probiotic products during past 1 month.

Exclusion Criteria:

1. Using mouth rinse routinely.
2. Undergoing any dental treatment during the study period.
3. Not able to brush their teeth and rinse on their own.

Study Design: Double Blind Randomized Controlled Trial.

Sample Size: Twelve participants will be chosen per group. With 3 products involved in each of the 2 population groups (children and elderly) the sample size will be 36 child participants and 36 elderly participants.

Consent from participants: Permission to conduct the study in the residential school and old age home will be obtained from the concerned authorities. Details about the study will be presented to the participants in the form of a study information sheet or communicated verbally in both English and in the local language. Only the eligible participants who provide written

consent will be included in the study. In case of children, written consent will be obtained from the guardians.

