Statistical Analysis Plan: Data will be analysed using SPSS (Statistical Package for the Social Sciences Version 22.0; SPSS Incorporated, Chicago, Illinois). Comparisons before and after interventions will be done using Paired t Test. Comparisons between Chlorhexidine, probiotic and xylitol groups will be done using ANOVA (Analysis of Variance) and Tukey's Post Hoc Tests. Comparison of antimicrobial efficacy of mouth rinses between children and elderly will be done using Independent sample t Test. Statistical significance will be fixed at $p \leq 0.05$.

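### The SAP fixes no scale for any test and no dependent variable for the ANOVA or the age comparison; analysing raw CFU/g could cost much of the power at 12 per arm

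*Combined protocol and SAP*

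**What the plan says.** The Statistical Analysis Plan is one paragraph. On the first two comparisons it says "Comparisons before and after interventions will be done using Paired t Test. Comparisons between Chlorhexidine, probiotic and xylitol groups will be done using ANOVA", followed by Tukey's tests. On the two populations it says "Comparison of antimicrobial efficacy of mouth rinses between children and elderly will be done using Independent sample t Test". Efficacy is not defined there as a variable, and the plan does not say whether the age test is run per rinse (12 v 12) or pooled over rinses (36 v 36).

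The outcome is defined only in Method, item 2: "The standard formula for determining Colony Forming Units (CFU) will be" colonies times dilution factor, divided by volume plated times plaque weight. The weight is obtained per sample ("The weight of the collected plaque (in grams) will be determined by subtracting the weight of the empty eppendorf tube"). On plating and counting, the text says "Similar dilutions will be prepared to obtain 1/10, 1/100 and 1/1000 dilutions" and "Bacterial colonies will be counted manually". There is no countable range and no rule for a plate with no colonies or with too many.

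The nearest statements to an endpoint are Objective 2, "To compare efficacies of the 3 mouth rinses in reducing" *S. mutans* levels, and Method, item 5, where "the same procedures will be repeated and compared with baseline". Neither gives a scale or says what enters the ANOVA. No transformation, baseline adjustment or rank-based alternative is mentioned.

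**The concern.** Every planned test compares means. Bacterial counts per gram can span orders of magnitude. If they do here, a few large values dominate the mean and the variance on the raw scale, and t tests and ANOVA become insensitive. With 12 per arm there is little to spare.

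The choice between day-14 value and change also matters far more on the raw scale. Falls of 1.5 and 0.5 log10 leave 10^-1.5 = 3.2% and 10^-0.5 = 31.6% of baseline, a tenfold contrast at day 14. The corresponding raw changes are 96.8% and 68.4% of baseline, a ratio of only 1.4, buried in the spread of baseline counts.

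At stake is Objective 2. A non-significant raw-scale ANOVA could be read as similarity to chlorhexidine when the same data on log10 would separate the rinses. Leaving the choice open also allows it to be made after the data are seen.

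**Working it through.** **Inputs from the document.** 12 per rinse within each population (12 x 3 = 36 children and 36 elderly, which agrees with Sample Size); significance at 0.05, taken as two-sided; dilutions 1/10 to 1/1000; 0.05 ml plated. The document gives no SD, baseline level, expected reduction or power, so there is no planned power figure to reproduce.

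**Assumptions.** Lognormal counts with equal log10 SD across arms (0.3, 0.5, 0.8 or 1.0); baseline to day-14 correlation 0.5; falls of 1.5, 0.5 and 0.5 log10, so that one rinse is tenfold better.

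**Step 1. Analytic check, log10 day-14.** The arm means deviate from their average by 2/3, 1/3 and 1/3, with sum of squares 4/9 + 1/9 + 1/9 = 2/3. The noncentrality is 12 x (2/3)/SD² = 8/SD², or 88.9, 32, 12.5 and 8. With F(2,33) the power is 100, 99.9, 86.5 and 67.5%.

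**Step 2. Simulated ANOVA power, all counts within assay limits.**

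| Analysis | SD 0.3 | SD 0.5 | SD 0.8 | SD 1.0 |
|---|---|---|---|---|
| Raw day-14 | 99% | 64% | 14% | 7% |
| Raw change | 16% | 7% | 3% | 2% |
| Log10 day-14 | 100% | 99.9% | 87% | 68% |
| Log10 day-14 adjusted for baseline | 100% | 100% | 94% | 79% |

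With two rinses better, raw day-14 gives 100/91/40/19%. With no true difference, raw analyses reject in 1.5 to 4.4% and log10 in about 5%, so the raw tests are conservative.

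**Step 3. Dependence on the correlation r.** Adjustment multiplies the residual variance by 1 - r²: 0.75 at r = 0.5, but 0.96 at r = 0.2. At r = 0.2 and SD 0.8, adjusted and unadjusted log10 power are 86.7 and 86.5%. Log10 change has variance factor 2(1 - r), which is 1.0 at r = 0.5 and 1.6 at r = 0.2, and its power drops to 66%.

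**Step 4. Paired t test, one arm, 0.5 log10 fall.** Raw 98/52/11/5%; log10 100/88/51/35%.

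**Step 5. Assay limits.** One colony on the 1/10 plate is 1 x 10/(0.05 x w) = 200/w CFU/g, where w is plaque weight in grams. An empty plate returns 0, which has no logarithm. A 300-colony limit (assumed; not in the document) on the 1/1000 plate is 300 x 1000/(0.05 x w) = 6,000,000/w. That is a factor of 30,000, or 4.48 log10, above the floor.

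If mean baseline is 5.5 log10 above the floor, 85 to 100% of baselines exceed this ceiling. With two rinses better, power at SD 0.8 and 1.0 is then 75 and 54% on raw day-14, 66 and 46% on log10 day-14, and 68 and 49% on baseline-adjusted log10. Kruskal-Wallis gives 75 and 54%. The advantage has reversed.

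**Step 6. Age comparison.** Both populations lose 90%, from baselines 0.5 log10 apart (assumed). Rejection rates at SD 0.3/0.5/0.8/1.0:

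| Setting | Raw change | Log10 change |
|---|---|---|
| Within limits, 12 v 12 | 88/33/7/3% | about 5% |
| Within limits, 36 v 36 | 100/80/22/9% | about 5% |
| Baselines 5.0 and 4.5 above floor, 12 v 12 | 17/8/6/5% | 90/40/14/9% |
| Baselines 5.0 and 4.5 above floor, 36 v 36 | about 42/14/6/6% | 100/85/32/18% |

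A censored-data likelihood model held 4.6 to 7.9% with baselines near or above the ceiling.

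**The case against.** The strongest reply is that the plan is merely silent. CFU/g is a laboratory formula, log10 analysis is compatible with every test named, and the power loss needs two unverified steps: raw analysis and roughly lognormal counts. This stands as far as it goes. A reader might infer that the SAP prescribes raw counts; it does not. But raw CFU/g is what a literal reading yields, and even an unadjusted log10 ANOVA leaves the collected baseline unused.

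A reader might also infer that no test has an endpoint. The paired t test has one by construction, day-14 minus baseline; only its scale is open.

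Nor is log10 always better. The loss on raw day-14 values is trivial at SD 0.3, and Step 5 shows a reversal when most baselines are uncountable. That ceiling is itself an assumption.

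On the age test, it is tempting to call the raw-change rejections false findings. They are not: equal percentage falls from different baselines are different absolute reductions, and raw change detects that correctly. It does not show different relative efficacy, and the document does not say which is meant.

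**Conclusion.** The point holds, with conditions. The gap is certain from the text: no scale for any test, no dependent variable for the ANOVA with Tukey or the age test, and no baseline adjustment. How much it costs is conditional. If counts are roughly lognormal and mostly countable, raw analysis is materially weaker from a log10 SD of about 0.5 upward, and raw change is very weak throughout the range examined. Log10 day-14 adjusted for baseline is the better method under those conditions, by a margin over unadjusted log10 that depends on the correlation.

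Because rinses are randomised and the raw tests are conservative, the document does not support a claim of inflated false positives between rinses. It should be fixed before analysis; confidence in the size is medium, since SD, baseline level and correlation are all unknown.

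**What to change.** In the Statistical Analysis Plan:

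- Compare rinses on day-14 log10(CFU/g) adjusted for baseline log10(CFU/g) by ANCOVA. Report multiplicity-adjusted pairwise geometric mean ratios with 95% confidence intervals.
- Run the before/after paired t test on log10 values.
- For children versus elderly, state whether the test is per rinse or pooled, and that relative reduction (log10 change) is the quantity of interest. If an appreciable share of baselines is uncountable, do not rely on log10 change; make a censored-data analysis primary.

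In Method, item 2:

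- Fix the countable range and the values entered for empty and uncountable plates, for example 100/w CFU/g (half the detection limit) for an empty plate.
- Report the number of such plates by arm and visit.
- Repeat the rinse comparison with a rank-based method, and rely on that repeat if many baselines are uncountable.

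No extra participants, samples or visits are needed. The costs are that results are read as ratios, the substituted values are conventions, a laboratory counting rule must be added, and the censored-data analysis may need software beyond the SPSS version named.

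### No test is named primary, and before-after paired t-tests, which cannot isolate a rinse effect without an untreated arm, share one threshold with the randomised rinse comparison

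*Combined protocol and SAP*

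**What the plan says.** The Statistical Analysis Plan lists three families of tests. The first is within-arm: "Comparisons before and after interventions will be done using Paired t Test". The second is ANOVA with Tukey's post hoc tests between the three rinses. The third is an independent-samples t-test between children and elderly. One rule covers all of them: "Statistical significance will be fixed at" p ≤ 0.05. No family is called primary, secondary or descriptive. The response analysed in the ANOVA (day-14 value or change) is not stated, nor is the scale.

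Under Randomization and Group allocation, every arm receives a rinse: "Group A will be given Chlorhexidine mouth rinse; Group B will be given Xylitol mouth rinse and Group C Probiotic mouth rinse". There is no placebo, water or untreated arm. The routine is common to all arms; under Intervention, "Mouth rinsing will be supervised during the study period by an assistant".

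The Aim is comparative: "To compare the antimicrobial efficacy of probiotic and xylitol mouth rinses with chlorhexidine (gold standard"), in children and the elderly. Objective 1 is to assess *S. mutans* at baseline and day 14. Objective 2 begins "To compare efficacies of the 3 mouth rinses in reducing". The two objectives are not ranked. Sample Size sets 12 per group, "With 3 products involved in each of the 2 population groups". The measurement is CFU per gram of plaque ("The standard formula for determining Colony Forming Units (CFU) will be" followed by the equation), taken at baseline and again after 14 days. No log transform is mentioned.

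**The concern.** A paired test asks whether the mean count in one arm changed over 14 days. It does not ask why. Anything acting on all participants alike would move every arm, for example being in a study, a supervised nightly routine, or differences between culture sessions. With no untreated arm, the paired test cannot remove such a change. The randomised between-rinse comparison can, because a common change cancels.

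Two misreadings are therefore open. A significant fall in an arm may be reported as proof that its rinse works. A significant fall in one arm and not in another may be reported as one rinse beating another, although no test of that difference has been made. Both reports would comply with the plan as written. Meanwhile the comparison that answers the Aim is the one left least specified, and the baseline count, already collected, has no stated role in it.

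**Working it through.** **The plan's own figure.** 12 × 3 rinses = 36 per population, and 36 × 2 = 72, as stated. No effect size, SD or power is given, so the 12 cannot be derived.

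**Inputs.** From the documents: n = 12 per cell, six cells (three rinses × two populations), threshold 0.05. Assumed, because the documents give none: two-sided tests, normal log10 counts with SD 0.6–0.8, baseline-to-day-14 correlation r 0.5–0.7, and a fall of 0.2 log10 in every arm with no difference between rinses.

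**Paired tests on log10.**
- SD of change = SD × √(2(1 − r)), and d = 0.2 / SD of change.
- The chance p of a significant reduction in one arm is the chance that a noncentral t (11 df, noncentrality d√12) exceeds 2.201.
- The chance of at least one in six independent arms is 1 − (1 − p)⁶.

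| SD | r | SD of change | d | p, one arm | at least one of six |
|---|---|---|---|---|---|
| 0.8 | 0.5 | 0.800 | 0.250 | 0.12 | 0.54 |
| 0.8 | 0.7 | 0.620 | 0.323 | 0.17 | 0.68 |
| 0.6 | 0.5 | 0.600 | 0.333 | 0.18 | 0.70 |
| 0.6 | 0.7 | 0.465 | 0.430 | 0.275 | 0.855 |

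Simulation of the same settings gives 0.540–0.860 for at least one of six.

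**Paired tests on raw CFU/g.** With raw = 10^x, simulation gives 0.158–0.452 for at least one of six. Per arm this is 1 − (1 − 0.158)^(1/6) = 0.028 to 1 − (1 − 0.452)^(1/6) = 0.095.

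**Sensitivity to the assumed fall** (at least one of six): at 0.1 log10, 31–48% on log10 and 9–20% on raw; at 0.3 log10, 77–99% and 26–72%.

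**Significant in one arm, not in another.** Within one population, the chance that one or two of the three arms, but not all, show a significant reduction is 1 − p³ − (1 − p)³. At p = 0.1215 this is 0.32; at p = 0.275 it is 0.60. The rinses are identical in this calculation.

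**Between-rinse ANOVA under the same fall.** The common shift cancels on log10. Two tests at 0.05 give 1 − 0.95² = 0.0975 for at least one false rinse difference. Simulation gives 0.094–0.100 on log10 and 0.033–0.057 on raw, so there is no rise with the fall.

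**Gain from using baseline.** Residual variance after adjustment is (1 − r²) × SD².
- Against day-14 values, the reduction is r²: 25% at r = 0.5 and 49% at r = 0.7.
- Against change scores, the ratio is (1 − r²) / (2(1 − r)) = (1 + r)/2: a reduction of 25% at r = 0.5 and 15% at r = 0.7.

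Simulated power for one rinse pair in one population (0.8 log10 difference, Tukey at 0.05) is 63–98% with adjustment. Without it, power is about 50–79% on day-14 values and about 50–96% on change scores. The low ends coincide because at r = 0.5 the SD of change equals the SD.

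**The case against.** The best defence is that the plan already points the right way. The Aim is purely comparative against a gold standard, Objective 2 compares the rinses, and ANOVA with Tukey is provided for it. Objective 1 only asks for levels at two times, which a paired test serves. This stands in part. A reader might infer that the plan gives paired tests equal authority, or lets them decide efficacy. The documents do not say so; they are silent on which test decides, and that silence is the defect.

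The any-of-six figure is also the most striking one available, and it rests on an assumed fall. This stands too: the per-arm figures are much lower. The documents offer little to size a common fall. Participants are selected on a caries-risk score that does not include the *S. mutans* count, so regression to the mean from selecting on the outcome is not built in. Rinsing, not brushing, is supervised. If all three rinses work, a common fall is a real effect. The point is that the paired test cannot tell these cases apart, not that any fall would be false.

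A second tempting reading is that the plan inflates the false-positive rate. With no true change in any arm, the chance of at least one false reduction or false rinse difference depends on choices the plan leaves open. With six paired tests and two ANOVAs it is 19–22% on log10 and 7–11% on raw CFU/g. With populations pooled it is 10–12% and 5–7%. At the low end there is essentially no inflation, so this cannot carry the point.

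Finally, with three active arms and no margin, making the rinse comparison decisive could invite a non-significant result to be read as equality with chlorhexidine. That is fair, and the fix must address it.

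**Conclusion.** The point holds as one of interpretation and specification. The plan ranks no test, no arm is untreated, and the comparison that answers the Aim lacks a stated response, scale and use of baseline. The logic needs no assumption: a within-arm test without a control cannot attribute a change to the rinse. Only the frequency of a misleading result rests on assumed values (SD, correlation and a 0.2 log10 common fall): about 12–27.5% per arm and 54–86% for any of six on log10, or 3–9.5% and 16–45% on raw CFU/g.

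The documents do not support saying that efficacy will be judged by the paired tests, that overall type I error is necessarily inflated, or that falls seen in this trial would be spurious. The randomised comparison is in the plan and remains sound. This should be corrected before unblinding, but it does not undermine the design.

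**What to change.** Name as primary the between-rinse comparison of day-14 log10 CFU/g adjusted for log10 baseline. Run it within children and within elderly, with all three rinse pairs compared by Tukey, or by Bonferroni if the software offers no Tukey with a covariate. Report within-arm change as a mean with 95% CI, stated to be descriptive and not evidence of rinse efficacy. State that a non-significant rinse difference is not evidence of equivalence to chlorhexidine, since no margin is set.

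Whether to split alpha between the two populations is the sponsor's choice. It should be stated before unblinding and is not part of the required change. Any convention for zero counts on the log scale is an implementation detail.

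The cost is SAP wording only, with no new data, visits or participants. Fewer results can be called significant. At 0.05 per population, baseline adjustment with Tukey raised power over both unadjusted log10 analyses in every setting checked. If alpha is split to 0.025 each, Tukey intervals widen by about 12% (studentized range 3.904/3.475 = 1.123). The largest power loss found is then about 5–6 points with Tukey and about 7 with Bonferroni (33% to 26%), for a 0.5 log10 difference against change scores at SD 0.8 and r 0.7.
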